### 2.2 Secondary objective

To determine the magnitude of BDV change in subjects who are subsequently diagnosed with severe infection.

Hypothesis being tested

- Null hypothesis: BDV in non-infected critically ill adult ICU subjects does not decrease significantly before a clinical diagnosis of severe infection.
- Alternative hypothesis: BDV in non-infected critically ill adult ICU subjects decreases significantly before clinical diagnosis of severe infection.

Hypothesis being tested

- Null hypothesis: BDV in the exhaled breath of critically ill adult ICU subjects is not a marker for response to treatment for infection.
- Alternative hypothesis: BDV in the exhaled breath of critically ill adult ICU subjects is a marker for response to treatment for infection.

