## **7.0 Data analysis and statistical considerations**

### **7.1 Sample size determination**

For trauma patients admitted to an ICU, the mean overall nosocomial infection rate is 6 to 18%. (9, 19, 20) The incidence rate of infection could be greater for all surgical ICU patients. Data collected to date indicate that a sustained decrease in BDV of 2.0‰ or more correlates with the onset of infection when the subject is used as his-her control. The average intra subject standard deviation (SD) across time points in 32 mechanically ventilated subjects previously studied was 1.16‰, regardless of the underlying medical conditions. The inter subject SD is expected to be 1.5‰ at most. Using the BDV measurements during the breath sample monitoring period (breath sample assessments every 4 hours), the expected overall SD of the mean BDV measurements (across time points) is less than 1.5‰.

Furthermore, during the monitoring period, the mean difference in the BDV between subjects who are diagnosed with a nosocomial infection and subjects not diagnosed with an infection is expected to be 2.0‰ or more (primary hypothesis). This difference will be considered to be the minimum difference with clinical importance.

Assuming that 5% of the subjects will have a confirmed nosocomial infection over the monitoring period and an overall standard deviation of 1.5‰, a total sample size of 100 subjects (5 infected and 95 non-infected) is required to detect a minimum clinically-important difference of 2.0‰ with at least 80% power at the two-sided 5% significance level.

If the actual rate of nosocomial infections is 10%, then the proposed total sample size of 100 subjects will provide 98% power to detect a mean difference of 2.0‰. Assuming SD to be 1.5‰ (at most) for the change in BDV before and after the diagnosis of an infection is made, a total sample size of 100 subjects and an infection rate of 5%, a mean decrease of 2.0‰ prior to and after the confirmed infection will be detected with 79% power at the one sided 5% significance level (secondary hypothesis).

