If the rate of nosocomial infections is 10%, then the mean decrease of 2.0‰ will be detected with 99% power. The proposed sample size of 100 subjects is sufficient to provide accuracy in estimating the specificity of the BDV analyzer. That is, with a sample size of 100 and assuming that 95% of the subjects will have no confirmed nosocomial infection, the specificity will be estimated with a standard error of less than 5%, and the 95% confidence interval of the estimated specificity will be no greater than 20%.

To account for a missing value rate -- due to study withdrawal (see 5.12 Withdrawal of subjects) or infection failure of up to 10%, the total enrollment target is 110.

***The goal sample size of 100 subjects will be achieved through implementation of the protocol at more than one approved study site.***

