## 5. Analysis Objectives

The overall objective of the analysis is to demonstrate that the BDV is a leading marker for infection diagnosis in critically ill subjects. Key questions to be answered are 1) Evaluate the BDV as a marker of infections in critically ill subjects at risk of progressing to severe sepsis and septic shock; 2) To measure variation of BDV with time in critically ill ICU patients progressing to severe sepsis and septic shock among those who agree to participate as research subjects; 3) To determine the magnitude of change of BDV in subjects who subsequently progress to severe sepsis and septic shock; 4) To define variation of BDV in critically ill ICU subjects who do not progress to severe sepsis and septic shock.

The BDV will be analyzed to determine the range of exhaled  $^{13}\text{CO}_2/^{12}\text{CO}_2$  BDV in adult subjects. The  $^{13}\text{CO}_2/^{12}\text{CO}_2$  BDV will be compared with current clinical standard scores, physiologic measurements and biomarkers (e.g. vital signs, WBC, CRP, PCT), and any interventions -- such as antibiotic administration -- will be noted for the purpose of assisting in understanding variation of BDV. For the purpose of defining a positive BDV for the presence of an infection, a positive BDV is defined as a change of greater than 1‰ within a 24-hour period above or below the baseline value. The 1‰ threshold for change in the BDV within 24 hours is based on the variability of approximately 0.5‰ seen in subjects with stable nutrition who do not develop infections. Thus, a change of 2 standard deviations away from the pre-infection mean will be examined as part of sensitivity among those with progression to severe sepsis and septic shock and positive predictive value for progression to severe sepsis and septic shock.

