For critically ill patients admitted to an ICU, the mean overall nosocomial infection rate is 6 to 18% (29, 30, 40). The incidence rate of infection could be greater for all surgical ICU patients. The infection rate in the previous proof-of-concept study was 50% using the same population and inclusion/exclusion criteria; this assumption of equal proportions of prospectively enrolled infected and uninfected subjects will be used in the sample size calculations which follow. Data collected to date indicate that a sustained change in BDV of 1.0‰ or more correlates with the presence of infection when the subject is used as his-her control. The average intra subject standard deviation (SD) across time points in critically ill adult subjects previously studied was 0.95‰, regardless of the underlying medical conditions. The inter subject SD is expected to be 1.0‰ at most. Using the BDV measurements during the breath sample monitoring period (breath sample assessments every 4 hours), the expected overall SD of the mean BDV measurements (across time points) is less than 1.0‰.

BDV sensitivity and specificity will be evaluated relative to PCT sensitivity and specificity according to non-inferiority hypothesis tests where a greater than 10% BDV disadvantage is to be ruled for both sensitivity and specificity relative to a less than 10% BDV disadvantage. The BDV sensitivity and specificity estimates will then be used to determine the positive predictive value (PPV) and negative predictive value (NPV) once the prevalence is known; prevalence surrogates can be used to apply the observed sensitivity and specificity to various ICU and CCU settings.

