### Hypotheses

#### Co-Primary Endpoint 1

1. Null hypothesis: BDV sensitivity is more than 10% worse than PCT sensitivity for progression to severe sepsis and septic shock in critically ill adult ICU subjects
2. Alternative hypothesis: BDV sensitivity is less than 10% worse than PCT sensitivity for progression to severe sepsis and septic shock in critically ill adult ICU subjects

#### Co-Primary Endpoint 2

1. Null hypothesis: BDV specificity is more than 10% worse than PCT specificity for those not progressing to severe sepsis and septic shock in critically ill adult ICU subjects
2. Alternative hypothesis: BDV specificity is less than 10% worse than PCT specificity for those not progressing to severe sepsis and septic shock in critically ill adult ICU subjects.

#### Secondary Endpoint 1

1. Null hypothesis: the variability of BDV in critically ill adult ICU subjects does not change after clinical diagnosis of progression to severe sepsis and septic shock.
2. Alternative hypothesis: the variability of BDV in critically ill adult ICU subjects increases after clinical diagnosis of progression to severe sepsis and septic shock.

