We will also categorize samples taken from a ventilator versus free-breathing patient for analysis. To assess the impact of collecting samples from the ventilator versus free breathing subjects, we examined breath samples right before and right after ventilator weaning. Eleven of our subjects have been ventilated at the beginning of our study and then extubated at some point during the study. Out of the eleven subjects who had enough data for the analysis, none showed significant changes in BDV after extubation, meaning that there were no differences between ventilated and free breathing values.

All analyses will be conducted under GCP and FDA 21 CFR 812 standards. SAS (SAS Institute, Cary NC) and StatXact (CyTel, Cambridge MA) will be used to conduct all analyses. All statistical testing will be two-sided using a 0.05 p-value to reach statistical significance.

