## 9. Statistical Methodology

Descriptive statistics will be generated. For continuous variables, descriptive statistics may include the number of subjects from whom data was used in the calculation, mean, standard deviation, median, minimum, and maximum; frequencies and percentages may be displayed for categorical data.

A 2-sample t-test will be used to compare the averaged (across time points) BDV between subjects who are diagnosed with an infection, without an infection, with sepsis and without sepsis. A linear mixed effects model with subject specific random effects will be used to compare BDV measurements between infected and non-infected and septic and non-septic subjects. This model will be also used to estimate the intra- and inter-subject variability of the BDV measurements. A paired t-test will be used to compare the BDV measurements prior to and after a diagnosis of infection or sepsis. Fisher's exact test and the Kappa statistic will be used to evaluate the relationship between a positive indication of infection by the BDV and a diagnosis of infection or sepsis in the subsequent 72 hours. Sensitivity, specificity, negative predictive value, positive predictive value and corresponding 95% confidence interval will be calculated.

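### The paired before/after BDV test is powered one-sided at 5% in the protocol, but the SAP makes all testing two-sided at 0.05 without an exception for it

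*Protocol*

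**What the plan says.** **Protocol 7.1 (sample size).** For the secondary hypothesis the protocol takes 100 subjects, 5% infected, a mean decrease of 2.0‰ and an SD of change of at most 1.5‰. It says this decrease "will be detected with 79% power at the one sided 5% significance level". If 10% are infected, "then the mean decrease of 2.0‰ will be detected with 99% power". The primary two-sample comparison in the same section is powered two-sided at 5%.

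**Protocol 7.2 (analysis plan).** A paired t-test of BDV before and after diagnosis is listed, with no sidedness.

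**SAP 6 and 9.** Both sections keep the test: "A paired t-test will be used to compare the BDV measurements prior to and after a diagnosis of infection or sepsis". Neither gives it a sidedness, an effect size or a power. SAP section 6 ends with a general rule: "All statistical testing will be two-sided using a 0.05 p-value to reach statistical significance". SAP section 10 declares no deviations.

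**Hypotheses.** Protocol 2.2 has the alternative that "BDV in non-infected critically ill adult ICU subjects decreases significantly before clinical diagnosis of severe infection". The SAP's only secondary endpoint has the alternative that "the variability of BDV in critically ill adult ICU subjects increases after clinical diagnosis" of progression to severe sepsis and septic shock. SAP objective 3 still asks for the magnitude of BDV change in subjects who later progress.

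**The concern.** Two documents governing one study set different significance levels for one test of a stated protocol hypothesis. If this is left open, whoever analyses the data can choose the level after seeing the result, and the same p-value can be reported as significant or not.

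The quoted power is also affected. 79% is the figure a reader would take as the study's ability to detect the within-subject drop in the planning case. It belongs to a one-sided 5% test, which the SAP as written does not allow.

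The purpose of the test is loosely tied as well. The test splits each subject's samples at diagnosis. Protocol 2.2 concerns a decrease that comes before diagnosis, and SAP Secondary Endpoint 1 concerns variability, which a paired t-test on means does not examine.

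**Working it through.** **Inputs (Protocol 7.1).** Mean decrease d = 2.0‰; SD of change s = 1.5‰ (stated as a maximum); n = 5 infected (5% of 100) or n = 10 (10%).

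**Formula.** Exact power of a paired t-test from the noncentral t distribution, with n − 1 degrees of freedom and noncentrality (d/s)·√n:

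- n = 5: (2.0/1.5)·√5 = 2.98, with 4 df
- n = 10: (2.0/1.5)·√10 = 4.22, with 9 df

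**Step 1: reproduce the protocol.** At one-sided 5%, power is the chance that the noncentral t exceeds the 95th percentile of central t.

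- n = 5: critical value 2.13, power 78.7% (stated 79%)
- n = 10: critical value 1.83, power 98.7% (stated 99%)

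Both figures reproduce. The primary two-sample figures do too, at two-sided 5%: 5 vs 95 gives 82.1% (stated at least 80%), and 10 vs 90 gives 97.7% (stated 98%).

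**Step 2: apply the SAP's rule.** At two-sided 5% the critical value is the 97.5th percentile: 2.78 for n = 5 and 2.26 for n = 10. Everything else is unchanged.

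| Infected | One-sided 5% | Two-sided 5% |
|---|---|---|
| 5 | 78.7% | 61.4% |
| 6 | 87.4% | 74.3% |
| 7 | 92.7% | 83.4% |
| 10 | 98.7% | 96.2% |
| 12 | 99.6% | 98.7% |

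Twelve infected is the middle of the 6–18% infection rate cited in Protocol 7.1.

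**Step 3: size of the disputed zone.** With 5 infected, a t statistic between 2.13 and 2.78 in the hypothesised direction passes at the protocol's level and fails at the SAP's. If the planning assumptions are true, the result lands there with probability 78.7% − 61.4% = 17.3%.

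**Step 4: sensitivity to the SD.** Because 1.5‰ is an upper value, a smaller SD helps. At an assumed 1.2‰, 5 infected give 79% power two-sided.

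**Step 5: is there an exception elsewhere in the SAP?** Its co-primary non-inferiority tests use one-sided 97.5% limits. Those leave 2.5% in the tail, the same as each tail of a two-sided 5% test, so they do not license a one-sided 5% test.

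**The case against.** **The effect is limited.** This is a secondary hypothesis in a study that calls itself a pilot. Two-sided power drops under 80% only at 5 or 6 infected, the protocol's cited rate is 6–18%, and 1.5‰ is a ceiling. One-sided 5% appears only in the protocol's power statement and not in its analysis plan, so the SAP's rule could simply be read as the operative one. All of this stands, and it keeps the point modest. It does not remove it: the stated 79% would then be wrong for the test to be run, and 5 infected is the case the protocol chose to plan on.

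**The SAP's two-sided sentence may be boilerplate,** given its own one-sided limits. That is possible, but it is the only sidedness rule in the SAP that covers the paired test.

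**Stronger readings that the documents do not support:**

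- *The protocol miscalculated.* It did not; its figures reproduce.
- *The one-sided test matches the directional hypothesis in Protocol 2.2.* Only loosely. That hypothesis concerns a fall before diagnosis, while the test splits at diagnosis.
- *The SAP gives competing inputs for this test.* The 97 events size the paired comparison of sensitivity with PCT. The rule that "a positive BDV is defined as a change of greater than 1‰ within a 24-hour period above or below the baseline value" defines a positive result. The SAP also says "Data collected to date indicate that a sustained change in BDV of 1.0‰ or more correlates with the presence of infection", but gives no SD of a paired change and no power for the paired t-test.
- *The test has lost its purpose in the SAP.* SAP objective 3 still covers magnitude of change, and SAP section 6 makes an own-control signal its first task.
- *The primary whole-stay comparison is underpowered because 2.0‰ was borrowed from an onset drop.* Protocol 7.1 also sets 2.0‰ as the minimum clinically important difference, which is a legitimate target. Its origin can only be inferred, since figures and part of the prior-study text are unavailable. The share of pre-onset samples is not given either.

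**Conclusion.** The conflict is real and the plan is wrong as written on this point: the protocol's power statement and the SAP's testing rule cannot both apply to the paired before/after test. On the protocol's inputs, power falls from 79% to 61% with 5 infected and from 99% to 96% with 10. This rests on a mean decrease of 2.0‰, an SD of change of 1.5‰, approximate normality of the changes and exactly 5 or 10 paired subjects.

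The practical weight is moderate to small. It matters most if few subjects are infected, and hardly at all from about 10 upward. No visible text says which document takes precedence or exempts this test; some SAP pages are missing from the public text, so that absence is judged on what can be read.

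**What to change.** Before the data are seen, make one of two changes:

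1. Make the paired test two-sided at 5% in both documents, and restate its power in Protocol 7.1 as 61% (96% at 10% infected).
2. Keep it one-sided at 5%, and name it in SAP section 6 as an exception to the two-sided rule.

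In either case, add a sentence saying which hypothesis or objective the test serves, given that it splits at diagnosis: the decrease before diagnosis in Protocol 2.2, or the magnitude of change in SAP objective 3. As a test of means, it does not address SAP Secondary Endpoint 1.

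The cost is wording only. Under option 1 the stated secondary power becomes less favourable.

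*Optional.* Whole-stay averages of infected subjects include samples taken before onset, because subjects enter without known or suspected infection and are sampled from enrollment. A supplementary version of the planned mixed model could carry time-varying infection status, switched at an onset date adjudicated by the endpoint committee (blinded to BDV) or at one pre-specified window before diagnosis. The planned two-sample t-test should stay. This adds some modelling and possibly one adjudication field. A fixed window would place some pre-drop samples in the infected period when the drop comes later.

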### **7.2 Analysis plan**

Descriptive statistics will be generated. For continuous variables, descriptive statistics may include the number of subjects from whom data was used in the calculation, mean, standard deviation, median, minimum, and maximum; frequencies and percentages may be displayed for categorical data.

A 2-sample t-test will be used to compare the averaged (across time points) BDV between subjects who are diagnosed with an infection, without an infection, with sepsis and without sepsis. A linear mixed effects model with subject specific random effects will be used to compare BDV measurements between infected and non-infected and septic and non-septic subjects. This model will be also used to estimate the intra- and inter-subject variability of the BDV measurements. A paired t-test will be used to compare the BDV measurements prior to and after a diagnosis of infection or sepsis. Fisher's exact test and the Kappa statistic will be used to evaluate the relationship between a positive indication of infection by the BDV and a diagnosis of infection or sepsis in the subsequent 72 hours. Sensitivity, specificity, negative predictive value, positive predictive value and corresponding 95% confidence interval will be calculated.

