### ***Enrollment***

A subject will be considered enrolled in the study once they have been consented for participation and the first breath sample has been collected. See study definitions in section 6.1.

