## **6. Analysis Sets/Populations/Subgroups**

The first task is to demonstrate that there is a positive signal associated with the Canary test using the subject as their own control.

A per protocol analysis will be performed following EAC event reconciliation and subsequent database lock. The EAC will determine diagnostic truth by documenting severe sepsis or septic shock events as well as the onset and resolution dates.

Infection documentation will be reviewed by the EAC committee based on best clinical practices, using four categories:

- No suspicion of infection
- Inconclusive evidence of infection
- High suspicion of infection
- Overt infection

For sensitivity and specificity, non-inferiority testing will be performed to rule out a -10% disadvantage according to a one-sided 97.5% lower confidence limit for the BDV – PCT

difference; exact McNemar paired comparison tests will be performed to test BDV non-inferiority relative to PCT. Both endpoints must achieve statistical significance in order to achieve study success.

PPV and NPV will be computed as observed and for a range of possible infection prevalence (10%, 20%, 30%, and 40%). Results will be analyzed in the same manner as sensitivity and specificity.

BDV variations will be assessed using a two-sample t-test to compare the averaged (across time points) BDV between subjects who are diagnosed with a severe sepsis and sepsis shock vs. no severe sepsis or sepsis shock. Also a linear mixed effects model with subject specific random effects will be used to compare BDV measurements between the two diagnostic groups. This model will be also used to estimate the intra- and inter-subject variability of the BDV measurements. A paired t-test will be used to compare the BDV measurements prior to and after a diagnosis of infection or sepsis.

The definition of a positive BDV will be based on a 72-hour window without advance knowledge of the diagnosis. In the absence of clinical details supporting PCT operating characteristics (sensitivity, specificity), two PCT thresholds (0.5 and 2.0) will be evaluated but the 0.5 threshold is deemed to be primary for BDV comparison.

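### The between-group comparison of BDV leaves out the enrolment BDV that every subject has; adding it as a covariate is a cheap gain in precision and protection against imbalance, mainly under the protocol's 5 versus 95 split

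*Protocol*

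**What the plan says.** **The between-group analyses.** Protocol 7.2 compares groups on one number per subject, BDV averaged over the stay: "A 2-sample t-test will be used to compare the averaged (across time points) BDV between subjects who are diagnosed with an infection". It adds a second analysis: "A linear mixed effects model with subject specific random effects will be used to compare BDV measurements between infected and non-infected". SAP 9 repeats both. SAP 6 applies both to severe sepsis or septic shock versus neither. Protocol 7.1 labels the infected versus non-infected difference the primary hypothesis and sizes the study on it. In the SAP the comparison is not a co-primary endpoint; those are the sensitivity and specificity of BDV relative to PCT.

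**The own-control premise.** Protocol 7.1 says that "a sustained decrease in BDV of 2.0‰ or more correlates with the onset of infection when the subject is used as his-her control". SAP 6 says: "The first task is to demonstrate that there is a positive signal associated with the Canary test using the subject as their own control".

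**The enrolment sample.** Protocol 4.2 (Enrollment) says: "A subject will be considered enrolled in the study once they have been consented for participation and the first breath sample has been collected". Known or suspected infection at enrolment is an exclusion in Protocol 3.1.2. The baseline covariates listed in SAP 7 do not include baseline BDV.

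**Own-control analyses elsewhere.** Protocol 7.2 and SAP 9 include one: "A paired t-test will be used to compare the BDV measurements prior to and after a diagnosis of infection or sepsis". The rule for a positive BDV is also a within-subject change. In Protocol 3.0 it is a sustained fall of about 2.0‰ over 24 hours; in SAP 5 it is a change of more than 1‰ from baseline within 24 hours.

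**The concern.** If infection shows itself as a change from the subject's own level, a comparison of raw levels carries noise that the design could remove. Subjects who start low and stay low look the same as subjects who fall.

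The mixed model as described does not repair this. A subject random effect accounts for correlation within a subject, but a group effect that is constant over time is still judged against between-subject variance.

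Two things are at stake. One is precision. Protocol 3.0 says the pilot's estimates will size the pivotal study, so a wider interval carries forward. The other is imbalance. With 5 infected subjects planned, a gap in starting level can add to or mask a response to infection, and because the groups are formed by outcome rather than by randomisation, such a gap need not be due to chance alone.

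**Working it through.** **Inputs.** From Protocol 7.1: difference 2.0‰; SD of the time-averaged BDV 1.5‰; inter-subject SD τ = 1.5‰ at most; intra-subject SD s = 1.16‰; 5 versus 95 subjects; two-sided 5%. From SAP 5: τ = 1.0‰ at most, s = 0.95‰, equal proportions infected and uninfected. The documents give no single number of samples per subject, so I assume m = 30 (5 days × 6 a day), with a range of 6 to 168 (28 days). I also assume independent within-subject errors and stable inter-subject differences, except where stated.

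**1. The plan's own power.** Two-sample t-test, noncentral t, SD 1.5‰:
- 5 versus 95: 82.1% (stated: at least 80%).
- 10 versus 90: 97.7% (stated: 98%).

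The paired test, one-sided 5%, SD of change 1.5‰, gives 78.7% for 5 subjects (stated 79%) and 98.7% for 10 (stated 99%). All four reproduce.

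**2. Where the noise in the t-test comes from.** Variance of a subject's mean = τ² + s²/m = 2.25 + 1.3456/30 = 2.295, so SD = 1.515‰. The between-subject share is 2.25/2.295 = 98%. With this SD, power for 2.0‰ at 5 versus 95 is 81%.

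**3. Adjusting for one enrolment sample.** Variance of a single sample = τ² + s² = 2.25 + 1.3456 = 3.596. Its covariance with the later mean is τ² = 2.25.
- Residual variance = 2.295 − 2.25²/3.596 = 2.295 − 1.408 = 0.887.
- Residual SD = 0.94‰; the variance falls by 61%.
- Power for 2.0‰ at 5 versus 95 = 99.6%.

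Over m = 6 to 168, unadjusted power is 78% to 82% and adjusted power 98.7% to 99.7%, so the choice of m hardly matters.

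**4. How far the gain depends on the inputs.**
- *Only half the inter-subject variance stable.* The covariance is 1.125. Residual variance = 2.295 − 1.125²/3.596 = 1.943, SD 1.39‰, power 87%.
- *Inter-subject SD 1.2‰ instead of the maximum.* Unadjusted SD = √(1.44 + 0.045) = 1.22‰, and unadjusted power is already 94%.
- *SAP SDs.* The SD falls from 1.015‰ to 0.71‰. At 50 versus 50, however, even a 1.0‰ difference has 99.8% power unadjusted, so there is practically nothing to gain in power.

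**5. Chance imbalance at 5 versus 95.** The standard error of the difference in true starting level is 1.5 × √(1/5 + 1/95) = 1.5 × 0.459 = 0.69‰. On a normal approximation, a gap of more than 1.0‰ either way, half the minimum important difference, has a probability of about 15%.

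**The case against.** **The signal is not lost.** A reader might infer that between-subject differences swamp it. The documents do not support that. The 1.5‰ used for sizing equals the maximum inter-subject SD, so the spread is already allowed for and the stated power holds.

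**Own-control analyses exist.** A reader might also infer that the plan never uses the subject as own control. It does, in the paired t-test and in the positive-BDV rule, which feeds the diagnostic accuracy measures and, in the SAP, both co-primary endpoints. This stands and limits the point. But the paired test uses only infected or septic subjects, so it cannot show that the others do not drift, and neither analysis changes the t-test or the mixed model.

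**Larger gains can be produced, but not from the documents.** Putting the SAP's SDs on the protocol's 5 versus 95 split gives 57% to 86% for a 1.0‰ difference, but it mixes two designs. With the protocol's SDs, a 1.0‰ difference gives 30% to 63%, but neither document sets 1.0‰ as a between-group target. It could arise if a 2.0‰ fall covered half the averaged period, and that loss would come as much from averaging samples taken before onset.

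**Baseline BDV is unnamed, not excluded.** The fixed effects of the mixed model are not listed, and SAP 7 and Protocol 3.0 foresee covariates. This is fair; the remedy is to name it.

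**Adjustment has its own risk.** The device is meant to react before symptoms, so an enrolment sample may already be shifted in subjects diagnosed soon afterwards, and adjusting would then remove some true effect. It also changes the estimand from the difference in levels in Protocol 7.1. Both points stand, and they are the reason to keep the unadjusted test alongside. The t-test's standard error does cover chance imbalance on average, but it does not correct the imbalance in the sample actually drawn.

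**Conclusion.** The point holds as a cheap improvement in efficiency and in protection against imbalance. It is not an error in the stated power. The comparison that sizes the protocol ignores a value that every subject has and that the own-control premise calls for.

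At the protocol's split and maximum inter-subject SD, adjustment takes power for 2.0‰ from 81% to over 99%. The realistic gain may be much smaller: to about 87% if half the inter-subject variance is stable, and from an unadjusted level of 94% if the inter-subject SD is 1.2‰. At the SAP's equal split the power gain is practically nil, and there the comparison is not co-primary.

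These figures rest on 30 samples per subject, independent errors and an enrolment sample taken before onset. Correlation between successive 4-hourly samples would change the SDs.

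**What to change.** In Protocol 7.2 and SAP 6 and 9:
- Make the between-group comparison an ANCOVA of mean post-enrolment BDV on infection group (in SAP 6, the severe sepsis or septic shock group), with enrolment BDV as covariate.
- Exclude the enrolment sample from the averaged outcome.
- Name the same covariate in the mixed model.
- Keep the unadjusted t-test as a supportive analysis.

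**Cost.** Wording in two documents and one degree of freedom; no new data. The downside is some attenuation if BDV had already changed at enrolment in subjects diagnosed soon afterwards. Reporting the unadjusted test beside the ANCOVA would show it.
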